8.6.4. Other Safety Evaluations

Vital signs and physical examination findings will be summarized at select time points. Study drug administration, study drug compliance, and other safety variables will also be summarized. Details will be provided in the statistical analysis plan.

8.7. Pharmacokinetic Analysis

The PK Analysis Set will be used for summaries of PK concentration of magrolimab versus time. Due to the sparse nature of PK collection, PK parameters will not be calculated.

Summary statistics will be presented for magnolimab serum concentrations at each scheduled time point. Descriptive graphical plots of individual serum concentration versus time profiles and mean concentration versus time profiles will be generated.

Missing concentration values will be reported as is in data listings. Concentration values below lower limit of quantitation will be handled as zero in summary statistics and reported as is in data listings.

All data from this study may be combined with PK data from other Gilead clinical studies and analyzed using a population PK model. Such an analysis would be reported separately.

8.8. Immunogenicity Analysis

Immunogenicity will be assessed using a 3-tier—screen, confirmatory, and titer—approach on study samples using a validated immunoassay. The rate and magnitude of anti-magrolimab antibody incidence, prevalence, persistence, and transience will be summarized for the Immunogenicity Analysis Set. Titer summaries may also be generated, if relevant.

8.9. Biomarker Analysis

The baseline level, absolute level, and change from baseline level over time will be summarized using descriptive statistics for each biomarker at the applicable sample collection time point by treatment cohort, as appropriate.

8.10. Sample Size

Sample size calculation is as follows:

 For Cohort 2, a sample size of 36 (30 patients in Phase 2 Cohort 2 together with 6 patients in Safety Run-in Cohort 2) provides an 83.1% power for a 1-group Chi-square test at 1-sided alpha of 0.1 level to detect a CR rate of ≥ 35% for the combination compared with a historical control CR rate of 19% {Greenberg 2004}.

The original protocol for the study included a Cohort 1, for which 46 patients were planned to be enrolled (6 patients in Safety Run-in and 40 patients in Phase 2); however, Cohort 1 was closed to enrollment following enrollment of 18 patients (7 patients in Safety Run-in and 11 patients in Phase 2).

The original protocol also included a Cohort 3, for which 46 patients were planned to be enrolled (6 patients in Safety Run-in and 40 patients in Phase 2); however, Cohort 3 was closed to enrollment and no patients were enrolled.

9. **RESPONSIBILITIES**

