1.1.2.2. Patients with Relapsed or Refractory AML after Induction Chemotherapy

Standard of care treatment for newly diagnosed AML patients who are eligible for induction chemotherapy consists of a combination of cytarabine and an anthracycline. Despite initial CR rates above 50% with induction chemotherapy, a substantial portion will be refractory to initial chemotherapy and a majority of patients will ultimately relapse, particularly those with poor-risk features. Treatment options in the relapsed/refractory (R/R) setting consist of salvage chemotherapy with a goal of undergoing allogeneic stem cell transplantation (SCT) for long-term remission. Various salvage chemotherapies are used in the treatment of R/R AML, including mitoxantrone, etoposide, and cytarabine (MEC); fludarabine, cytarabine, idarubicin, and granulocyte colony-stimulating factor (G-CSF); and G-CSF, clofarabine, and cytarabine. With all of these agents, the CR rates range from 15% to 25%, with a median OS of approximately 3 to 5 months {Feldman 2005, Greenberg 2004}.

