3.1.2. Phase 2 Cohorts

After completion of each safety run-in cohort and identification of the RP2D for that cohort, the corresponding Phase 2 cohort may be enrolled as follows:

- Phase 2 Cohort 1 (1L Unfit AML Mag+Ven+Aza), closed to enrollment globally as of *Protocol Amendment 5*: 40 patients with newly diagnosed, previously untreated AML who are ineligible for intensive chemotherapy will be enrolled to receive magrolimab + venetoclax + azacitidine
- **Phase 2 Cohort 2 (R/R AML Mag+MEC):** 30 patients with R/R AML will be enrolled to receive magrolimab + MEC.
- Phase 2 Cohort 3 (Post-chemo Maint Mag+CC-486), closed to enrollment globally as of *Protocol Amendment 5*: 40 patients with newly diagnosed AML who are in CR or CRi with MRD positivity following intensive chemotherapy may be enrolled to receive magrolimab + CC-486.

Up to 5 to 10 additional patients may be enrolled in each of the Phase 2 cohorts to collect additional safety, efficacy, and/or PK/PD data.

3.1.3. Closure of Cohorts 1 and 3

Cohort 1 closed to enrollment globally as of Protocol Amendment 5 and no new patients enrolled in Cohort 1 thereafter. A total of 18 patients were enrolled into Cohort 1 (7 patients in safety run-in and 11 patients in Phase 2).

Cohort 1 patients enrolled prior to sponsor's notification and implementation of Protocol Amendment 5 will continue on study, receive study treatment (Sections 3.3, 5.1, and 5.2), and undergo all study assessments (Section 6), until end of study or discontinuation criteria are met (Sections 3.4 and 3.5).

Cohort 3 closed to enrollment globally as of Protocol Amendment 5 and no patients were enrolled.

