8.5. Efficacy Analysis

8.5.1. Primary Analysis

The point estimates of the CR rate and the corresponding 2-sided exact 95% CIs based on the Clopper-Pearson method will be provided for Cohorts 1 and 2. The MRD negative CR rate will be summarized similarly for Cohort 3. The CR and MRD negative CR data will also be tested against the historical control rates listed in Section 8.10 using 1-group Chi-square test for each cohort separately.

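### Cohort 2: the stated pair of one-sided alpha 0.10 and 83.1% power is a large-sample figure that no responder cutoff delivers at n = 36 (10 or more CRs gives 13.1% / 86.2%; 11 or more gives 6.6% / 76.6%)

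*Protocol*

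**What the plan says.** Protocol Section 8.10 plans Cohort 2 on "a sample size of 36 (30 patients in Phase 2 Cohort 2 together with 6 patients in Safety Run-in Cohort 2"). It says that this number "provides an 83.1% power for a 1-group Chi-square test at 1-sided alpha of 0.1 level", and the contrast is "to detect a CR rate of ≥ 35% for the combination compared with a historical control CR rate of 19" per cent. The synopsis repeats the statement.

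Section 8.5.1 makes the same procedure the analysis: the CR data are to be "tested against the historical control rates listed in Section 8.10 using 1-group Chi-square test for each cohort separately". It also plans an interval estimate: "The point estimates of the CR rate and the corresponding 2-sided exact 95% CIs based on the Clopper-Pearson method".

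Neither section names an exact test, a continuity correction or a critical number of responders. Section 3.1.2 leaves the final number open: "Up to 5 to 10 additional patients may be enrolled in each of the Phase 2 cohorts".

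**The concern.** With 36 patients and a null rate of 19%, the expected number of CRs under the null is 36 × 0.19 = 6.84. At that size the binomial distribution moves in coarse steps. A nominal alpha of 0.10 and a power read from a continuous normal curve may then be far from what the test actually does. If the real rejection rule has a type I error above 10%, the cohort is more lenient than the protocol says. If the rule is tightened to hold 10%, its power is lower than the protocol says.

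This matters because Cohorts 1 and 3 are closed to enrolment, and Cohort 2 is the only cohort for which Section 8.10 still gives a test and a power. The cohort has no concurrent control, so the comparison with 19% carries the whole inferential weight.

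**Working it through.** **Inputs (Sections 8.10 and 8.5.1).** n = 36; p0 = 0.19; p1 = 0.35; one-sided alpha 0.10, so z = 1.2816; 1-group chi-square test with no correction named.

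**Step 1: reproduce the stated power.**
- Standard error under the null: √(0.19 × 0.81 / 36) = 0.0654.
- Standard error under the alternative: √(0.35 × 0.65 / 36) = 0.0795.
- Critical rate: 0.19 + 1.2816 × 0.0654 = 0.2738.
- Power: Φ[(0.35 − 0.2738) / 0.0795] = Φ(0.959) = 0.831.

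This matches 83.1%. Other common formulas do not: continuity-corrected 78.3%, arcsine 81.7%, alternative variance only 76.8%, null variance only 87.8%. The figure therefore comes from the uncorrected large-sample formula.

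**Step 2: find the actual rejection rule at n = 36.** The critical count is 36 × 0.2738 = 9.86.
- 9 of 36 (25.0%): z = (0.2500 − 0.19) / 0.0654 = 0.92, one-sided p = 0.179, not rejected.
- 10 of 36 (27.8%): z = (0.2778 − 0.19) / 0.0654 = 1.34, one-sided p = 0.090, rejected.

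The test as written therefore rejects at 10 or more CRs.

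**Step 3: exact binomial properties of the neighbouring cutoffs,** with X ~ Bin(36, p).

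| Reject if CRs ≥ | Type I error, P(X ≥ r given 0.19) | Power, P(X ≥ r given 0.35) |
|---|---|---|
| 9 | 0.2335 | 0.9275 |
| 10 (chi-square as written) | 0.1308 | 0.8615 |
| 11 (smallest that holds 0.10) | 0.0657 | 0.7657 |
| 12 | 0.0296 | 0.6437 |

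No row has type I error of at most 0.10 together with power of 0.831. The rule as written exceeds its level by 3.1 points, a relative excess of 0.1308 / 0.10 − 1 = 31%. The rule that holds the level falls short of the stated power by 83.1 − 76.6 = 6.5 points.

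**Step 4: does it depend on n?** The same calculation at sizes that the optional enrolment could produce:

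| n | Uncorrected chi-square rejects at | Exact type I error | Exact power | Smallest cutoff holding 0.10 |
|---|---|---|---|---|
| 36 | ≥ 10 | 13.1% | 86.2% | ≥ 11 |
| 37 | ≥ 11 | 7.8% | 79.9% | ≥ 11 |
| 38 | ≥ 11 | 9.2% | 82.9% | ≥ 11 |
| 39 | ≥ 11 | 10.7% | 85.6% | ≥ 12 |
| 40 | ≥ 11 | 12.3% | 87.9% | ≥ 12 |
| 41 | ≥ 12 | 7.5% | 82.4% | ≥ 12 |
| 46 | ≥ 13 | 8.3% | 86.8% | ≥ 13 |

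The chi-square test's true level moves up and down with n. A cutoff fixed at 11 also stops holding 10% from n = 39.

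**The case against.** The strongest reply is that nothing was miscalculated. The protocol gives a nominal alpha and an approximate power, and 83.1% is what the usual formula returns for the test it names. That is correct, and a reader who inferred an arithmetic slip would be wrong. What remains is that the approximation is presented as the property of a 36-patient test, and it is not.

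A second reply is that the excess depends on two things: exactly 36 patients and no continuity correction. Both limits are real. At n = 38 the uncorrected test gives 9.2% and 82.9%, close to the stated pair. With a continuity correction, 10 of 36 gives p = 0.129 and 11 of 36 gives p = 0.060, so the rule becomes 11 or more CRs. A statistical analysis plan, not shown here, could specify that. But 36 is the planned number, and the stated power matches the uncorrected formula. Under a correction the level is safe, but the power at n = 36 is 76.6%, so the stated pair is still not met.

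Three stronger readings are tempting, and the documents do not support them.
- A reader might infer that the exact 95% interval contradicts the test, because its lower limit stays below 19% at 10, 11 and 12 CRs. A two-sided 95% interval and a one-sided 0.10 test work at different error levels, so such counts are expected. Section 8.5.1 gives the interval as estimation, not as a success criterion. An exact test would leave the same gap at 11 and 12 CRs.
- A reader might apply the top of the range in Section 1.1.2.2 ("the CR rates range from 15% to 25" per cent) as the true control rate and report a much larger false-success probability. That range covers several salvage regimens together. For MEC itself, Sections 1.4.4 and 1.6.2 give about 20%, close to the 19% null. The choice of historical rate is also a separate question from the error rates of the test.
- A reader might treat this as a threat to a trial decision. No section ties a go/no-go, stopping or success rule to the test in this uncontrolled Phase 2 cohort.

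**Conclusion.** The point stands as an issue of operating characteristics. At n = 36 the test as written has exact type I error 13.1% and power 86.2%. The smallest cutoff that holds 10% has type I error 6.6% and power 76.6%. No integer cutoff gives the stated 10% with 83.1%. The practical difference falls on one result, 10 CRs of 36, where the chi-square test rejects and an exact test at the same level does not.

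This rests on three assumptions: independent binary responses, the uncorrected form of the test (which the 83.1% implies), and an analysis of 36 patients with the 6 run-in patients pooled as Section 8.10 describes. On the 30 Phase 2 patients alone, the uncorrected test rejects at 9 or more CRs, with 10.04% and 77.5%. The realised number may also differ from 36: Section 3.1.2 allows extra patients, and Section 4.1.1 replaces run-in patients who are not evaluable for DLT, while the Full Analysis Set keeps everyone dosed.

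The severity is should-fix: a stated figure and one possible conclusion are affected, but no stated decision depends on them.

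**What to change.** In Section 8.5.1, Section 8.10 and the synopsis:

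1. Replace the 1-group chi-square test with an exact one-sided binomial test of the CR rate against 19% at alpha 0.10, applied at the realised number of Cohort 2 patients in the Full Analysis Set.
2. Replace the power statement with the exact planned properties at n = 36: reject at 11 or more CRs, exact type I error 0.066, power 76.6% at a true CR rate of 35%.
3. State that the cutoff is recomputed from the binomial distribution if the number analysed is not 36, including when the optional extra patients are enrolled. A cutoff of 11 must not be carried forward: its exact type I error is 10.7% at n = 39 and 12.3% at n = 40.

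The cost is wording in three places and a stated power of 76.6% in place of 83.1%. No extra patients, visits or data are needed. The exact test would also follow the same binomial method that Sections 8.3.2 and 8.5.1 already use for the intervals.

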9.1. Investigator Responsibilities

9.1.1. Good Clinical Practice

The investigator will ensure that this study is conducted in accordance with the International Council for Harmonisation (ICH) E6(R2) addendum to its guideline for GCP and applicable laws and regulations.

9.1.2. Financial Disclosure

The investigator and subinvestigators will provide prompt and accurate documentation of their financial interest or arrangements with Gilead, or proprietary interests in the study drug during the course of a clinical study. This documentation must be provided prior to the investigator's (and any subinvestigator's) participation in the study. The investigator and subinvestigator agree to notify Gilead of any change in reportable interests during the study and for 1 year following completion of the study. Study completion is defined as the date when the last patient completes the protocol-defined activities.

[figure not shown]
9.1.3. Institutional Review Board/Independent Ethics Committee Review and Approval

The investigator (or Gilead as appropriate according to local regulations) will submit this protocol, ICF, and any accompanying material to be provided to the patient (such as advertisements, patient information sheets, or descriptions of the study used to obtain informed consent) to an IRB/IEC. The investigator will not begin any study patient activities until approval from the IRB/IEC has been documented and provided as a letter to the investigator.

Before implementation, the investigator will submit to and receive documented approval from the IRB/IEC any modifications made to the protocol or any accompanying material to be provided to the patient after initial IRB/IEC approval, with the exception of those necessary to reduce immediate risk to study patients.

9.1.4. Informed Consent

The investigator is responsible for obtaining written informed consent from each individual participating in this study after adequate explanation of the aims, methods, objectives, and potential hazards of the study before undertaking any study-related procedures. The investigator must use the most current IRB- or IEC-approved ICF for documenting written informed consent. Each ICF (or assent as applicable) will be appropriately signed and dated by the patient or the patient's legally authorized representative, the person conducting the consent discussion, and an impartial witness (if required by IRB or IEC or local requirements).

9.1.5. Confidentiality

The investigator must ensure that patients' anonymity will be strictly maintained and that their identities are protected from unauthorized parties. Only an identification code and any other unique identifier(s) as allowed by local law (such as year of birth) will be recorded on any form or biological sample submitted to Gilead, IRB/IEC, or the laboratory. Laboratory specimens must be labeled in such a way as to protect patient identity while allowing the results to be recorded to the proper patient. Refer to specific laboratory instructions. NOTE: The investigator must keep a screening log with details for all patients screened and enrolled in the study, in accordance with the site procedures and regulations. Patient data will be processed in accordance with all applicable regulations.

The investigator agrees that all information received from Gilead, including but not limited to the IB, this protocol, case report forms (CRFs)/eCRFs, study drug information, and any other study information, remains the sole and exclusive property of Gilead during the conduct of the study and thereafter. This information is not to be disclosed to any third party (except employees or agents directly involved in the conduct of the study or as required by law) without prior written consent from Gilead. The investigator further agrees to take all reasonable precautions to prevent the disclosure by any employee or agent of the study site to any third party or otherwise into the public domain.

9.1.6. Study Files and Retention of Records

The investigator must maintain adequate and accurate records to enable the conduct of the study to be fully documented and the study data to be subsequently verified. These documents should be classified into at least the following 2 categories: (1) investigator's study file, and (2) patient clinical source documents.

The investigator's study file will contain the protocol/amendments, CRFs/eCRFs, IRB/IEC and governmental approval with correspondence, the ICF, drug records, staff curricula vitae and authorization forms, and other appropriate documents and correspondence.

The required source data should include sequential notes containing at least the following information for each patient:

- Patient identification
- Documentation that patient meets eligibility criteria, ie, medical history, physical examination, and confirmation of diagnosis (to support inclusion and exclusion criteria)

- Documentation of the reason(s) a consented patient is not enrolled
- Participation in study (including study number)
- Study discussed and date of informed consent
- Dates of all visits
- Documentation that protocol-specific procedures were performed
- Results of efficacy parameters, as required by the protocol
- Start and end date (including dose regimen) of study drug, including dates of dispensing and return
- Record of all AEs and other safety parameters (start and end date, and including causality and severity) and documentation that adequate medical care has been provided for any AE
- Concomitant medication (start and end date; dose if relevant; dose changes)
- Date of study completion and reason for early discontinuation, if it occurs

All clinical study documents must be retained by the investigator for at least 2 years or according to local laws, whichever is longer, after the last approval of a marketing application in an ICH region (ie, US, Europe, or Japan) and until there are no pending or planned marketing applications in an ICH region; or, if no application is filed or if the application is not approved for such indication, for 2 years after the investigation is discontinued and regulatory authorities have been notified. Investigators may be required to retain documents longer if specified by regulatory requirements, by local regulations, or by an agreement with Gilead. The investigator must notify Gilead before destroying any clinical study records.

Should the investigator wish to assign the study records to another party or move them to another location, Gilead must be notified in advance.

If the investigator cannot provide for this archiving requirement at the study site for any or all of the documents, special arrangements must be made between the investigator and Gilead to store these records securely away from the site so that they can be returned sealed to the investigator in case of an inspection. When source documents are required for the continued care of the patient, appropriate copies should be made for storage away from the site.

9.1.7. Case Report Forms

For each patient consented, an eCRF casebook will be completed by an authorized study staff member whose training for this function is completed in the electronic data capture (EDC) system. The eCRF casebook will only capture the data required per the protocol schedules of assessments. The Inclusion/Exclusion Criteria and Enrollment eCRFs should be completed only

after all data related to eligibility have been received. Data entry should be performed in accordance with the CRF Completion Guidelines provided by the sponsor. Subsequent to data entry, a study monitor will perform source data verification within the EDC system. System-generated or manual queries will be issued in the EDC system as data discrepancies are identified by the monitor or Gilead staff who routinely review the data for completeness, correctness, and consistency. The site investigator, site coordinator, or other designee is responsible for responding to the queries in a timely manner, within the system, either by confirming the data as correct or updating the original entry, and providing the reason for the update (eg, data entry error). Original entries as well as any changes to data fields will be stored in the audit trail of the system. At a minimum, prior to any interim time points or database lock (as instructed by Gilead), the investigator will use his/her log-in credentials to confirm that the forms have been reviewed, and that the entries accurately reflect the information in the source documents. At the conclusion of the study, Gilead will provide the site investigator with a read-only archive copy of the data entered by that site. This archive must be stored in accordance with the records retention requirements outlined in Section 9.1.6.

9.1.8. Investigator Inspections

The investigator will make available all source documents and other records for this study to Gilead's appointed study monitors, to IRBs/IECs, or to regulatory authority or health authority inspectors.

9.1.9. Protocol Compliance

The investigator is responsible for ensuring the study is conducted in accordance with the procedures and evaluations described in this protocol.

9.2. Sponsor Responsibilities

9.2.1. Protocol Modifications

Protocol modifications may be made only by the sponsor.

9.2.2. Study Reports and Publications

A clinical study report (CSR) will be prepared and provided to the regulatory agencies when applicable and in accordance with local regulatory requirements. Gilead will ensure that the report meets the standards set out in the ICH Guideline for Structure and Content of Clinical Study Reports (ICH E3). Note that an abbreviated report may be prepared in certain cases. For studies with sites in countries following the EU Regulation No. 536/2014, a CSR will be submitted within 1 year (6 months for pediatric studies, in accordance with Regulation [EC] No. 1901/2006) after the global end of study (as defined in Section 3.5).

Investigators in this study may communicate, orally present, or publish study data in scientific journals or other scholarly media in accordance with the Gilead clinical trial agreement.

